6. STORAGE, HANDLING, AND DISPENSING

6.1. All chemotherapy agents are commercially available and will be stored handled and dispensed per institutional protocols.

6.2. The use of Etoposide, Ifosfamide, and Carboplatin in this trial are approved use of FDA approved drugs. When a drug or combination of drugs are used in such a manner as part of a clinical trial, it is by rule, considered as an investigational treatment regimen. However, while these treatment regimens are not approved by the FDA, their use is exempt from the requirements for an IND to conduct this study as defined under Title 21, CFR 312.2(b) of the codified FDA regulations.

7. DOSE MODIFICATIONS

7.1. All toxicities should be graded according to the Common Terminology Criteria for Adverse Events (CTCAE), version 4.0.

7.2. Dose modifications are based on dose level administered on the last treatment day. Dose adjustments of each agent may be made independently based on the specific toxicities observed.

7.3. Blinding/Unblinding is not applicable to this protocol.

8. STUDY ASSESSMENTS AND PROCEDURES

| | Baseline | Day -5 to +14 or Discharge (Daily unless stated otherwise) | After Discharge: Weekly until stable | Day 30 | Day 100 | Every 3 – 6 months | 1 Year | Yearly until 5 years from transplant |
|---|----------|--|--------------------------------------|--------|---------|------------------------------|--------|--------------------------------------|
| H&P with VSS | X | X | X | X | X | X | X | X |
| Performance Status | X | X | X | X | X | X | X | X |
| AE Assess | | X | X | X | X | X | | |
| ECG, ECHO, and/or MUGA Scan, and/or Cardiac MRI | X | | | | | | X | yearly if abnormal |
| PFT's | X | | | | | | X | yearly if abnormal |
| CBC & Diff | X | X | X | X | X | X | X | X |
| PT/PTT/INR | X | | | | | | | |
| BMP, Mg, Phos | X | X | X | X | X | X | X | X |
| LFT's, LDH | X | Weekly | X | X | X | | X | X |
| TFT's (TSH, free T4) | X | | | | | | X | X |
| IgG | X | | | X | X | | X | |
| CD4, CD8 | | | | X | X | | X | |
| CT or MRI Primary / Metastatic Site | X | | | | X | X (at 6 months and 9 months) | X | X |
| PET Scan | X | | | | X | X (at 6 and 9 months) | X | X |

| | | | | | | | | |
|-----------------------------|---|--|--|--|--|--|---|--|
| Audiogram | X | | | | | | X | |
| Creatinine Clearance or GFR | X | | | | | | | |
| DEXA Scan | | | | | | | X | |

9. SAFETY ASSESSMENTS

- 9.1.** Subjects must undergo a history and physical examination by a licensed provider daily while in hospital and at each follow-up visit.
- 9.2.** Laboratory testing should be completed as outlined in the study schedule. Additional laboratory testing may be done at the Investigator's discretion.

10. EFFICACY ASSESSMENTS

- 10.1.** Tumor response will be assessed using MRI/CT/PET imaging of the primary site and known metastatic sites.
- 10.2.** Measureable disease: the presence of at least one measurable lesion that can be accurately measured in at least one dimension (the longest diameter) and with a minimum size of 10 mm by CT or MRI scan.
- 10.3.** Non-measurable lesions: all other lesions including leptomeningeal disease, pleural/pericardial effusion, and blastic bone lesions.
- 10.4.** All measurements should be recorded in metric notation, using a ruler or calipers using the same method of assessment to characterize each identified and reported lesion at baseline and during follow-up.
- 10.5.** All baseline evaluation should be performed as close as possible to the initiation of conditioning treatment and not more than 30 days before conditioning treatment begins.
- 10.6.** Response Criteria include:

11. Response Criteria for Patients with Solid Tumors

This study will use a modified version of the Response Evaluation Criteria in Solid tumor (RECIST) from the NCI to evaluate disease response. The modifications will include volumetric measurement of the primary NPC and assessment of associated adenopathy. Measurable and non-measurable metastatic foci in the lungs, bones and liver will be evaluated as per RECIST.

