15.2 Analysis of the Primary Endpoint

PFS is defined as the time from treatment start to the first of either (1) documented disease progression or (2) death as a result of any cause. Patients who did not progress nor die or are lost to follow-up will be censored at the day of their last objective tumor assessment. The Kaplan-Meier method will be used to estimate the median PFS time, together with a 95% confidence interval (CI). PFS will be determined by MRI imaging.

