15.3 Analysis of Secondary Endpoints

The objective RR is equal to the proportion of patients achieving a best overall response of partial or complete response (CR + PR), according to imaging from the start of the treatment until disease progression/recurrence. Clinical benefit rate is equal to the objective RR plus the proportion of patients attaining stable disease (CR + PR + SD). Patients who do not have a tumor response assessment for any reason will be considered nonresponders and will be included in the denominator when calculating the response rate. The number of patients achieving a response will be divided by the total of patients treated to yield the proportion responding. Exact confidence bounds (95% CI) will be calculated.

Overall survival is defined as the time from the date of treatment start to the date of death from any cause. If the patient is alive at the end of the follow-up period or is lost to follow-up, OS will be censored on the last date the patient is known to be alive. OS will be evaluated by the Kaplan-Meier method and a 2-sided 95% CI will be provided for the median OS.

Time to progression (TTP) for responders only is measured from the time measurement criteria are first met for CR/PR (whichever is first recorded) until the first date that the criteria for PD are met, or death. TTP will be

estimated with the Kaplan-Meier method; a 90% CI will be provided for the median TTP. Patients who do not relapse are censored at the day of their last objective tumor assessment. The freedom from metastasis rate is defined below and will be calculated based on an intention to treat principle. Determination of the anatomic site of first failure for patients with PD will be recorded and analyzed. Duration of response is also defined below.

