15.5 Duration of Response and other Endpoint Definitions

The duration of overall response is measured from the time measurement criteria are met for CR or PR (whichever is first recorded) until the first date that recurrent or progressive disease is objectively documented (taking as reference for progressive disease the smallest measurements recorded since the treatment started), or death.

The duration of overall CR is measured from the time measurement criteria are first met for CR until the first date that recurrent disease is objectively documented, or death.

Stable disease is measured from the start of the treatment until the criteria for progression are met, taking as reference the smallest measurements recorded since the treatment started.

Rate of freedom from metastasis (FFM) is defined as the proportion of patients with documentation of progression of disease, during study participation, in whom no new lesions appeared.

In rare situations where PD or other endpoints could not be clearly assessed, the PI will review the records with the treating physician and provide a clinical judgment for purposes of endpoint documentation.

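### The protocol gives conflicting accounts of which body regions and which scans count when a new lesion is found, so progression at a new site can go uncounted or be dated late

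*Combined protocol and SAP*

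**What the plan says.** Some passages are narrow:

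- Section 10.1: "Tumor response will be assessed using MRI/CT/PET imaging of the primary site and known metastatic sites". PET stands in the same list as CT and MRI, so the word *known* applies to it too.
- Section 15.2: "PFS is defined as the time from treatment start to the first of either (1) documented disease progression or (2) death as a result of" whatever cause. The same section then names MRI alone as the way PFS is determined, with no body region given.

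Others are wider:

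- Section 8 has a row for "CT or MRI Primary / Metastatic Site", without the word *known*. A separate PET row names no site: "PET Scan | X | | | | X | X (at 6 and 9 months) | X | X". Both rows fall at baseline, Day 100, 6 and 9 months, 1 year and then yearly to 5 years.
- Section 11: "This study will use a modified version of the Response Evaluation Criteria in Solid tumor (RECIST) from the NCI to evaluate disease response". It adds: "Measurable and non-measurable metastatic foci in the lungs, bones and liver will be evaluated as per RECIST". It does not restrict these to foci present at baseline.

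Two secondary analyses depend directly on new lesions being found. Section 15.5 defines freedom from metastasis, among patients with documented progression, as the share "in whom no new lesions appeared". Section 15.3 says: "Determination of the anatomic site of first failure for patients with PD will be recorded and analyzed". No passage states that a new lesion is progression. That follows only from the reference to RECIST.

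**The concern.** An endpoint that turns on new lesions needs two things fixed in advance: where one looks, and which scans count. Here the section on efficacy assessment ties the assessed sites to what was known at entry, and the primary endpoint section ties PFS to one modality. Two patients in the same cohort could then be searched differently because of their disease at baseline, and two readers could date the same patient's progression differently.

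An uncounted or late-dated new lesion lengthens PFS. It can raise freedom from metastasis. It also distorts site of first failure, because a locoregional failure may be recorded first when the distant one came earlier. In a single-arm pilot of 10 there is no comparator arm in which the same error would occur.

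**Working it through.** The plan has no figure to reproduce: Section 15.1 sets 10 patients on availability, without power or alpha. The main check is to set the passages side by side.

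| Section | Regions | Modality | New lesions |
|---|---|---|---|
| 8, CT/MRI row | primary and metastatic | CT or MRI | silent |
| 8, PET row | none stated | PET | silent |
| 10.1 | primary and known metastatic | MRI, CT, PET | silent |
| 11 | primary, adenopathy, lung, bone, liver | not stated | only through RECIST |
| 15.2 | none stated | MRI only | only through documented progression |
| 15.3, first failure | wherever PD occurs | not stated | site analysed |
| 15.5, freedom from metastasis | any | not stated | defines the endpoint |

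**A test case.** A patient enters with recurrence in the neck only, and the 6-month PET shows a new lung lesion. Sections 8 and 11 support counting it. Under 10.1 the lung is not a known site. Under 15.2 the lesion was not seen on MRI. The same scan is progression by one route and not by the other. Section 8 also permits CT instead of MRI, so a patient followed by CT may have no MRI on which to determine PFS.

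**PFS.** A lesion visible at 6 months and recorded at 12 adds 12 − 6 = 6 months to that patient's PFS. It must also go unrecorded at the 9-month visit. If it is recorded there, the delay is 9 − 6 = 3 months.

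**Freedom from metastasis.** I use the denominator in 15.5, patients with documented progression, although 15.3 also invokes intention to treat. Assume 5 true progressors, of whom k have no new lesion, and suppose one of the others is never documented as progressing. The rate goes from k/5 to k/4, a rise of k/20:

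| k | All 5 documented | One lost | Rise (points) |
|---|---|---|---|
| 0 | 0% | 0% | 0 |
| 1 | 20% | 25% | 5 |
| 2 | 40% | 50% | 10 |
| 3 | 60% | 75% | 15 |
| 4 | 80% | 100% | 20 |

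A rise of 20 points for every k needs a different case: the patient stays in the denominator through progression elsewhere while the new lesion is missed, (k + 1)/5 − k/5 = 20 points. If the lesion is found late but is found, the rate does not change.

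**Response.** Section 15.3 uses best overall response up to progression. A CR or PR scored at Day 100 stands whatever happens at 6 months, so a later missed relapse moves the rate by 0 points. Only a new lesion already present when best response is scored can change it. One such patient is 1/10 = 10 points, for example 5/10 (exact 95% CI 18.7% to 81.3%) instead of 4/10 (12.2% to 73.8%).

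**How likely is one case?** The documents give no rate. Let p be the assumed chance that a patient's first progression lies only at a new site outside 10.1. The chance of at least one such patient in 10 is 1 − (1 − p)^10: 40% at p = 5%, 65% at 10%, 89% at 20% and 97% at 30%. This is the chance that the situation arises, not that the lesion is missed.

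**The case against.** The strongest reply is that new metastases are within the plan. The PET row has no site limit, the CT/MRI row omits *known*, Section 11 covers lung, bone and liver foci by RECIST, and the definitions in 15.3 and 15.5 show that new lesions were expected to be found and counted. Section 10.1 speaks of tumour response and does not define progression. Section 15.5 also allows the PI, with the treating physician, to resolve unclear endpoints by clinical judgment.

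Most of this stands, and it rules out the stronger reading that a reader might take from 10.1 alone: that new distant metastases fall outside tumour assessment and would be missed until symptoms appear. No passage says that a new lesion seen on PET is ignored.

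It does not remove the conflict. Scheduling a PET does not say what its findings count for, and its field of view is not stated. Section 11 says how foci are evaluated, not that those organs are imaged in a patient with no known disease there. The MRI sentence in 15.2 applies to the primary endpoint without exception. The judgment clause is reserved for rare, unclear cases, whereas a plain new lesion on PET is clear in itself and lacks only a rule.

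It is also fair to say that a pilot of 10 with no hypothesis test rejects or accepts nothing on these numbers. That limits the consequence, but the estimates are what the study will report.

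**Conclusion.** The point holds as an inconsistency. Sections 8, 10.1, 11 and 15.2 disagree on the regions and modalities that count for new lesions, and the two narrower passages, followed literally, let a lesion seen only on PET or CT go uncounted or be dated late. This goes beyond missing detail, because the MRI-only rule governs the primary endpoint.

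The size is that of single patients: 6 months of PFS for one patient, if the lesion also goes unrecorded at 9 months, and 0 to 20 points on freedom from metastasis, if 5 patients truly progress and one is never documented.

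Three further inferences are not supported. A missed relapse does not in general move the response rate by 10 points, because best response already scored is kept. The shift in freedom from metastasis is not a flat 20 points. The errors do not all run in the regimen's favour: for site of first failure the effect is distortion, not benefit.

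**What to change.** - **10.1:** state that each imaging visit, baseline included, assesses the primary site, known metastatic sites and all regions covered by the PET already scheduled. Baseline needs the same coverage, or a later lesion cannot be called new.
- **15.2:** replace the MRI-only sentence so that PFS may be determined by MRI, CT or PET. A new-lesion rule added beside the present sentence would leave the contradiction in place.
- **10.1 and 15.2:** state that an unequivocal new lesion at any site is progression on the date of that scan. Count an equivocal PET focus only if later imaging, scheduled or clinically indicated, confirms it, and say which date is then used. After year 1 the next scheduled scan may be a year away, so using the confirmation date would bring back the delay.

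The cost is wording. No scan is added, provided the scheduled PET is not itself confined to known sites. The protocol does not give its field of view, so this should be checked first; if it is confined, wider coverage is a real addition. The downside is that PFS and freedom from metastasis may look slightly less favourable, and some PET foci will be false positives, which the confirmation rule limits but does not remove.

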12. ADVERSE EVENT REPORTING

12.1. An adverse event (AE) is defined as any new untoward medical occurrence or worsening of a pre-existing medical condition in a patient or clinical investigation subject administered an investigational (medicinal) product and that does not necessarily have a causal relationship with this treatment. An AE can therefore be any unfavorable and unintended sign (including an abnormal laboratory finding) symptom, or disease temporally associated with the use of the investigational product, whether or not considered related to the investigational product.

12.2. *Serious Adverse Events* – any untoward medical occurrence that at any dose:

- Results in death
- Is life-threatening (defined as an event in which the subject was at risk of death at the time of the event; it does not refer to an event which hypothetically might have caused death if it were more severe)
- Requires inpatient hospitalization or causes prolongation of existing hospitalization
- Results in persistent or significantly disability/incapacity
- Is a congenital anomaly/birth defect
- Is an important medical event, defined as a medical event that may not be immediately life threatening or result in death or hospitalization but, based on appropriate medical and scientific judgment, may jeopardize the subject or may require intervention (eg. medical, surgical) to prevent one of the other serious outcomes listed above.
- All pregnancies, regardless of outcome must be reported including pregnancies that occur in the female partner of a male subject. All pregnancies must be followed to outcome.

12.3. *Non-serious Adverse Events* –all adverse events that are not classified as SAE's.

12.4. All adverse events, including those that are serious will be graded according to the National Cancer Institute Common Terminology Criteria for Adverse Events (NCICTCAE, Version 4.0).

12.5. The following categories and definitions of causal relationship to investigational product as determined by a physician should be used:

- 1 **Related** – there is a reasonable causal relationship to the investigational product administration and the adverse event.

2 **Not Related** – there is not a reasonable causal relationship to investigational product administration and the adverse event.

12.6 SAE Reporting: All grade 3 non-hematologic SAE's must be collected, including those thought to be associated with protocol-specified procedures. Collection of all SAEs must continue for 60 days after the last administration of the investigational products. All SAE's must be reported to UF-IRB-01 within 5 working days.

12.7 Laboratory Test Abnormalities – all laboratory test results captured as part of the study should be recorded following institutional procedures. In general, non-clinically significant laboratory deviations are not considered adverse events. Laboratory deviations which require treatment delay, modification or discontinuation or are otherwise clinically significant should be reported as adverse events.

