13. DATA SAFETY MONITORING PLAN

This protocol will adhere to the policies of the UF Health Shands Cancer Center Data and Safety Monitoring Plan, in accordance with NCI regulations. The Data and Safety Monitoring Committee will review all serious adverse events and toxicity reports as well as annual reviews. The investigator will continuously monitor the progress of the study and the safety of the participants. All adverse events will be evaluated for causality and reported to the appropriate oversight committees as required.

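### Section 12.6 states two scopes for SAE collection: grade 3 non-hematologic events in its first sentence, all SAEs in the rest of the section, in 12.2 and in section 13

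*Combined protocol and SAP*

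**What the plan says.** Section 12.6 has three sentences on SAEs. The first says which must be collected: "All grade 3 non-hematologic SAE's must be collected, including those thought to be associated with protocol-specified procedures". The second sets the duration: "Collection of all SAEs must continue for 60 days after the last administration of the investigational products". The third sets reporting: "All SAE's must be reported to UF-IRB-01 within 5 working days". Only the first names a grade or an organ class.

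Section 12.2 defines an SAE by what happens to the patient. It begins "any untoward medical occurrence that at any dose" and lists outcomes, among them "Results in death" and "Is life-threatening (defined as an event in which the subject was at risk of death at the time of the event". Hospitalization or its prolongation, disability and important medical events are also on the list. Pregnancy sits in the same list with its own duty: "All pregnancies, regardless of outcome must be reported including pregnancies that occur in the female partner of a male subject". Section 12.4 applies CTCAE version 4.0 grades to every adverse event, serious ones included.

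Section 13 gives the oversight remit: "The Data and Safety Monitoring Committee will review all serious adverse events and toxicity reports".

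**The concern.** The first sentence of 12.6 is where study staff will look to learn which SAEs to record, and it is the narrowest statement of scope in the protocol. Taken at face value, it does not reach SAEs of any grade other than 3, and it does not reach hematologic SAEs at all. No passage says that grade 3 is shorthand for grade 3 and above, or that hematologic SAEs are exempt.

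This matters for three reasons. Toxicity is one of the trial's two specific aims (3.2). Pancytopenia is the first risk listed for the treatment in 5.5.6.2, so the hematologic class is not marginal. And with 10 patients planned (5.2, 15.1), the monitoring committee will be judging safety on few events, so a gap in the SAE record would be hard to absorb.

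**Working it through.** There is no figure to reproduce. The check is a comparison of scope.

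| Place | What it governs | Grade limit | Organ-class limit |
|---|---|---|---|
| 12.6, first sentence | which SAEs to collect | grade 3 | non-hematologic |
| 12.6, second sentence | how long to collect | none | none |
| 12.6, third sentence | what goes to the IRB | none | none |
| 12.2 | what counts as an SAE | none (set by outcome) | none |
| 13 | what the committee reviews | none | none |

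One row of five differs. The next question is whether the other rows settle it. That depends on what *all SAEs* means in the second and third sentences of 12.6.

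1. **It means every event that meets 12.2.** This is the more natural reading, because 12.2 is where the term is defined. The first sentence is then a subset of the other two. It adds nothing to them and puts a narrower scope in the place where the collection rule is expected.
2. **It means all of those just named.** Section 12.6 then agrees with itself but not with its surroundings. Section 12.2 classes deaths and life-threatening events as SAEs whatever their grade or organ class, and section 13 has the committee review all SAEs, yet 12.6 would require collection of only some of them.

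The text needs reconciling under either reading. The first leaves a misleading sentence, and the second leaves a conflict with 12.2 and section 13.

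The events outside the first sentence, read literally, are:

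- any hematologic SAE, whatever its grade;
- any fatal or life-threatening event not graded 3;
- any SAE of a lower grade, such as one that is serious because it prolonged a hospital stay;
- pregnancies, which 12.2 places in the SAE list with no grade condition.

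The protocol does not print the CTCAE scale, and the argument does not need it. It is enough that 12.4 grades serious events, so that a grade limit has a practical effect, and that 12.2 sets no grade.

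**The case against.** The strongest reply is that the sentence requires one set of SAEs to be collected and does not exempt the rest. That is correct: the word *only* does not appear. The same paragraph then requires collection of all SAEs to continue for 60 days and sends all SAEs to the IRB. A careful site would collect everything.

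A reader might infer that the protocol excludes fatal and hematologic SAEs, and that the toxicity results for Aim 3.2 will therefore be understated. The documents do not support either step, because the toxicity analysis does not rest on this sentence:

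- Section 15.4 bases safety on reported AEs, examinations, laboratory tests and ECGs. It tabulates AEs by worst CTCAE grade with no lower limit and no hematologic exemption, and adds laboratory shifts to worst grade.
- Section 8 schedules a CBC with differential daily from Day -5 to Day +14 or discharge, weekly after discharge until stable, and at Day 30 and Day 100. Hematologic toxicity therefore has its own source of data.
- Section 13 also has all adverse events assessed for causality and passed to the oversight committees as required.
- Death from any cause is an event in PFS (15.2) and OS (15.3), so deaths are recorded in any case.

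These safeguards stand, and they limit the consequence. They do not remove the defect. Most of them protect the AE tables, the laboratory tables and the survival endpoints, not the SAE record itself. The cover from 15.4 is also shorter than the SAE window, because that section leaves out of the analysis any AE more than 30 days after the last dose, while 12.6 collects SAEs to 60 days.

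**Conclusion.** Section 12.6 contains a contradictory statement of scope that should be corrected. It is a wrong collection sentence, not a missing detail. It is also not a clear exclusion of severe events. The risk is that a site treating the first sentence as the operative rule leaves fatal, life-threatening, lower-grade or hematologic SAEs out of the record that the committee reviews. This assumes a literal reading by the site and no correction from the two sentences that follow. The documents do not show that this has happened or will happen.

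The size cannot be stated as a probability. The protocol gives no rate of severe events. A rate could be assumed and turned into the chance of at least one such event among 10 patients, but that would be the chance that an event occurs, not the chance that one is missed. The only firm scale is the sample size: in any SAE proportion reported on 10 patients, one patient wrongly counted as free of SAEs moves the result by 1/10, or 10 percentage points.

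**What to change.** Delete the words *grade 3 non-hematologic* from the first sentence of 12.6 and tie the sentence to the definition. It would then require collection of all SAEs as defined in 12.2, of any grade, hematologic or non-hematologic. The existing clause on events linked to study procedures stays as it is. The second and third sentences of 12.6 and section 13 need no change.

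If a grade threshold or a hematologic exemption was intended for non-serious adverse events, state it in a separate sentence and align it with 15.4, which has no such limit now. Two additions are best avoided. Summary logging of expected cytopenias would reopen a hematologic exemption unless *expected* is defined. A new rule for grade 3 and higher AEs could be read as a lower limit on what 15.4 tabulates.

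The cost is one sentence and some more hematologic SAE entries across 10 patients, in a setting where cytopenia is a listed risk. The change concerns data collection only and touches no dose or clinical management rule.
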